- f Assessment of measurable disease by imaging will be done according to SOC, i.e., during screening (up to 8 weeks prior to enrollment) and at approximately 3 and 12 months during follow-up. The 12-month (+/- 1-month post completion of radiation therapy or BMX-001 treatment) follow-up imaging for this study will be a chest x-ray and is required as part of this study protocol and is specifically for research purposes.
- g For BMX-001, Day -4 to 0 will be the loading dose.
- h For BMX-001, doses (50% of the loading dose) will be twice a week subcutaneously weeks 1-8.
- ⁱ Cisplatin 100mg/m² IV q21 days starting Day 1 for 2-3 doses or 30-40mg/m² IV per institutional standard each week of treatment x 6-7 total doses.
- ^j Female patients only: pregnancy test (serum beta-HCG) no more than 48 hours prior to first dose of BMX-001.
- ^k Radiation therapy may extend into week 8. This is allowable and there is no limitation for radiation therapy extending into the 8th week of BMX-001 treatment.

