13.1 Evaluations During Treatment

13.1.1 Treatment Period

The treatment period consists of 6-7 weeks of concurrent RT and chemotherapy with BMX-001 followed by 1-2 weeks of BMX-001 (BMX-001 extends to week 8).

Physical examinations, vital signs (temperature, respiratory rate, blood pressure, and pulse), height (screening or baseline only), and weight must be performed at:

- screening
- baseline
- every week from weeks 1-8
- at each SOC visit after completing RT for a period of 1 year

More frequent examinations may be performed.

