13.7 Outcomes Criteria

13.7.1 Time-to-Event Variables

Progression-free survival (PFS) is defined as the time between initiation of protocol treatment and the first recurrence of disease or death.

Overall survival will be defined as the time to death from the time of study enrollment.

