14.3 External Data and Safety Monitoring Board (DSMB)

The sponsor and Principal Investigators are responsible for overseeing the safety and efficacy of the trial, executing the DSM plan, and complying with all reporting requirements to local and federal authorities. Additional oversight will be carried out by an external DSMB.

An external DSMB will be utilized to monitor the Phase 1/Phase 2 clinical trial of BMX-001. This DSMB will be organized to meet requirements of Western IRB, the institutional IRBs, and the NCI. We anticipate a charter with a minimum of 3 members, which may include: a radiation oncologist, a medical oncologist both with expertise in head and neck cancer, a biostatistician, and/or an ethicist or patient advocate. The DSMB will hold an initial meeting to review the final protocol before enrollment of the first patient. The responsibilities of the DSMB will be to review safety of study procedures, to maintain study integrity, to review adverse events and to review efficacy of the outcome data. The DSMB will meet either face to face or by teleconference at least semi-annually and on an ad hoc basis as indicated by any adverse events. Minutes will be kept of both open and closed meetings of the DSMB. At the end of the study, all minutes taken will be available to the clinical trial principal investigators, the NCI, and BioMimetix JV, LLC.

During Phase 2 of the trial, the sponsor will notify the DSMB within 48 hours of any reported grade 3-5 DLT deemed probably or definitely related to BMX-001.

The DSMB's responsibilities will include evaluation of treatment outcome for evidence of tumor protection by the study drug. If the DSMB determines that there is substantial evidence of excess tumor progression in the presence of the study drug, the DSMB will have authority to recommend closure of the clinical trial.

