Kaplan-Meier methods will be used to graphically describe the distribution of overall survival (OS) and progression-free survival. OS is defined as the time interval between initiation of protocol treatment and death, with overall survival censored at last follow-up if the patient remained alive. PFS is defined as the time between initiation of protocol treatment and disease progression or death. If the patient remains alive without disease progression, then PFS will be censored at last follow-up. Median OS and PFS, as well as 6- and 12-month estimates of OS and PFS will be estimated from the Kaplan-Meier curve.

2. To assess radiographic response in locally advanced HNSCC patients treated with standard RT and cisplatin with BMX-001 at MTD.

The radiographic response (CR or PR) will be assessed as defined in 12.6.2. The radiographic response rate will be tabulated and reported using frequencies and 95% confidence intervals.

16.2.2.3 **Exploratory Objectives for Phase 2**

1. To further describe patient-reported outcomes of HRQoL in locally advanced HNSCC with standard RT, cisplatin, and BMX-001 at the MTD.

16.2.3 Interim Analysis for Phase 2

No interim efficacy analyses are planned given the length of time to assess an individual patient's outcome and the expected rapidity of patient accrual.

16.2.4 Sample Size Calculation for Phase 2

In this study, patients will receive BMX-001 at the Recommended Phase 2 Dose (RP2D). The ultimate goal of this study is to determine whether BMX-001 in combination with standard RT and cisplatin treatment is worthy of further investigation. The cohort will be compared with historical controls, which will be assessed for quality.

We will focus on the occurrence and severity of mucositis, xerostomia, and radiation dermatitis in this power calculation given that the study is not a randomized study, even though we are interested in comparing groups with respect to change in mucositis and xerostomia between protocol timepoints.

We anticipate accruing 48 patients which, for statistical purposes, we assume that approximately 40 will have available measurements of mucositis, xerostomia, and radiation dermatitis. We use a conservative estimate of a proportion of 0.50 since it results in the widest CI. A sample size of 40 produces a two-sided 95% exact confidence interval (Clopper-Pearson) with a width equal to 0.324 when the sample proportion is 0.50.

17 References

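### Twelve-month PFS is counted from treatment start but read before the 12-month disease assessment, which is counted from the end of treatment, so the estimate is biased upward by an amount the documents do not fix

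*Combined protocol and SAP*

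**What the plan says.** **The PFS clock.** Section 16.2.2.2 says "PFS is defined as the time between initiation of protocol treatment and disease progression or death". Section 13.7.1 uses the same origin: "Progression-free survival (PFS) is defined as the time between initiation of protocol treatment and the first recurrence of disease or death". The landmarks are read on that clock: "Median OS and PFS, as well as 6- and 12-month estimates of OS and PFS will be estimated from the Kaplan-Meier curve". On censoring, Section 16.2.2.2 says "If the patient remains alive without disease progression, then PFS will be censored at last follow-up".

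**The assessment clock.** Footnote f to the Section 13 schedule says "The 12-month (+/- 1-month post completion of radiation therapy or BMX-001 treatment) follow-up imaging for this study will be a chest x-ray". Section 13.7.2 gives the usual standard-of-care (SOC) scans as 3 months (plus or minus 2 weeks) and 12 months (plus or minus 1 month) from the end of RT. Footnote b sets the minimum post-therapy visits: within 1 month of completing RT (or BMX-001), then at 6 and 12 months after radiation, each plus or minus 1 month.

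**The gap between the clocks.** Footnote g says "For BMX-001, Day -4 to 0 will be the loading dose". Section 13.1.1 says "The treatment period consists of 6-7 weeks of concurrent RT and chemotherapy with BMX-001 followed by 1-2 weeks of BMX-001", with BMX-001 running to week 8. Footnote k allows RT to run into week 8. Section 9.6 tolerates RT breaks of up to 10 treatment days in total.

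The documents contain no rule that re-anchors the 12-month landmark, backdates a progression found at a late assessment, or treats progression times as interval-censored.

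**The concern.** Both schedules use the label 12 months, but they count from different days. If the last scheduled look at the disease always comes after month 12 on the PFS clock, a progression that arose earlier and is first seen at that look is dated after the landmark. The patient then counts as progression-free at month 12. The error has one direction: it makes 12-month PFS look better.

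PFS is one of the measures named under the Phase 2 secondary efficacy objective. The DSMB's remit in Section 14.3 also includes "evaluation of treatment outcome for evidence of tumor protection by the study drug". For a drug meant to protect normal tissue from radiation, an optimistic PFS figure errs on the less cautious side.

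**Working it through.** **The plan's own figures.** The documents give no PFS rate, PFS power or PFS sample size. The only computed design figure is the exact interval width in Section 16.2.4. For 20 of 40 the Clopper-Pearson limits are 0.338 and 0.662, a width of 0.324, as stated. It has no bearing on PFS timing.

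**Step 1: treatment start to end of treatment** (1 month = 30.44 days).
- Shortest: 30 weekday fractions from a Monday, with no lead time, take 39 days, or 39 / 30.44 = 1.28 months.
- Longest without breaks: loading dose on day -4 and treatment to the end of week 8 (day 56) take 60 days, or 60 / 30.44 = 1.97 months.
- With breaks: 35 fractions plus 10 missed weekdays end about day 61. From day -4 that is 65 days, or 65 / 30.44 = 2.14 months.

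**Step 2: assessments moved to the PFS clock.**

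| Assessment | Earliest (months) | Latest (months) |
|---|---|---|
| 3-month scan, ±2 weeks | (91.3 − 14 + 39) / 30.44 = 3.8 | (91.3 + 14 + 60) / 30.44 = 5.4 |
| 6-month visit, ±1 month | 5 + 1.28 = 6.3 | 7 + 1.97 = 9.0 |
| 12-month visit and imaging, ±1 month | 11 + 1.28 = 12.3 | 13 + 1.97 = 15.0 |
| Same, with permitted RT breaks | – | 13 + 2.14 = 15.1 |

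The 3-month scan precedes month 6. No in-window 12-month assessment precedes month 12. For one to do so, RT would have to end within about 30 days of treatment start (12 − 11 = 1 month).

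**Step 3: size of the bias, under assumptions.** Take a constant hazard, S(t) = S(12)^(t/12), and a 3-month scan at month 4.6, the middle of its range. Let q be the share of all PFS events found only at scheduled imaging. Deaths and clinically found recurrences make up the rest and are dated on time. Then

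bias at month 12 = q × [S(4.6) − S(12)].

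For S(12) = 0.75, S(4.6) = 0.896 and the bracket is 0.146:
- q = 10%: +1.5 points
- q = 25%: +3.6 points
- q = 50%: +7.3 points

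At q = 50%, the bias is +9.9 points for a true 65% and +4.5 points for a true 85%.

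If the 6-month visit (about month 7.6) found every such progression present by then, S(7.6) = 0.833. The bracket becomes 0.083, and the bias is +0.8 points at q = 10% and +4.2 at q = 50%.

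**Step 4: what a 15-month landmark leaves.** Take the 12-month assessment at month 13.5, near its nominal time. With the same curve, S(13.5) = 0.724 and S(15) = 0.698. The residual is q × 0.026: +0.3 points at q = 10% and +1.3 at q = 50%.

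**The case against.** The case on the other side has real force.

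- **Scans do not define PFS events.** Section 13.7.1 counts recurrence or death. The RECIST-type criteria in Section 13.7.2 concern radiographic response and apply only to definitive-intent patients. Section 13.1.1 provides physical examinations at each SOC visit for a year after RT, and unscheduled scans are not excluded. This stands: it limits the bias but does not remove it, because the last minimum visit before month 12 falls at 6.3 to 9.0 months.
- **The share q has no source in the documents.** This stands, so no single figure can be defended. For scale, with 48 patients and a PFS of 75%, the approximate 95% half-width is 1.96 × √(0.75 × 0.25 / 48) = 12 points, larger than any bias computed above. A systematic error of known direction is still worth removing when only wording is needed.
- **The required 12-month image is a chest x-ray.** It does not show the primary site or the neck, so it cannot be what first reveals a locoregional recurrence. This stands. Late locoregional detection would come from the visit's history and general physical examination or from SOC neck imaging.
- **The stakes are modest.** PFS is not a listed Phase 2 endpoint (Sections 5.2 and 16.2.1). The secondary objective names median PFS. No test or decision rule uses the 12-month value, and the full curve will be shown.

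A reader might infer that the mismatch would hide tumor protection from the DSMB, or would tilt a historical comparison towards BMX-001. The documents support neither. Section 14.3 does not tie the board's review to 12-month PFS, and the board meets at least semi-annually. The historical comparison in Section 16.2.2.1 is attached to mucositis, xerostomia and dermatitis; Section 16.2.4 mentions historical controls for the cohort in general, and no PFS comparison is specified.

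**Conclusion.** The mismatch follows from the documents' own dates, and its direction is certain: as written, 12-month PFS is read before the assessment that shares its name and is biased upward. This holds for patients who complete planned RT and are assessed in window; it is not a claim about every possible patient or an out-of-window scan.

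The size is conditional. For a true 12-month PFS of 75% and a constant hazard, it is about +1 to +2 points if 10% of events are found only at scheduled assessments. It is about +7 if 50% are and the 3-month scan was the last effective look, and nearer +4 if the 6-month visit catches what is present by then.

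A reader might also infer that PFS as a whole is unreliable. That goes too far: deaths and clinically detected recurrences before month 12 are dated correctly, month 6 has a scan before it, and 12-month OS, the primary endpoint and the sample size are untouched.

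**What to change.** In Section 16.2.2.2:

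1. Report PFS at 15 months from treatment initiation as the landmark that includes the 12-month assessment. Keep 6-month PFS and 12-month OS.
2. If 12-month PFS is kept for comparability, label it as preceding that assessment.
3. State that the follow-up of about 24 months after RT in Section 13.3 is used for PFS, so that progression-free patients are not censored at the 12-month visit, and report the number at risk at month 15. This condition is essential. If each patient left the risk set at that visit, either as an event or as censored, the risk set would shrink across the window while events continued, and the Kaplan-Meier estimate at month 15 would be unstable and biased low.
4. State that locoregional status at the 12-month visit comes from the history and physical examination and any SOC neck imaging, and that the required chest x-ray informs thoracic and distant status only. Section 13.1.2 describes a general physical examination, so the text should not refer to a dedicated head and neck examination.

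This changes wording only and adds no visit or scan. The cost is a lower reported PFS at a less customary time point. A small upward bias remains for progression arising between the assessment and month 15 (about 0.3 to 1.3 points in the example above), and a patient with the maximum RT breaks could be assessed just after month 15.

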4.1.2 Radiation-induced Damage

Radiotherapy for the treatment of head and neck cancers can produce severe therapy-induced side effects. Acute effects commonly appear within a week of starting radiotherapy and most people suffer from at least one of these unwanted side effects. The acute side effects can include: xerostomia, mucosal degradation (mucositis) and ulceration, edema, loss of taste (dysgeusia), difficulty swallowing and talking, ear aches, infections, hair loss, and radiation dermatitis. These acute problems can become so severe that radiation therapy has to be delayed, which can lead to reduced local control or at times, terminated. Long-term complications from radiation therapy directed to the head and neck region can include trismus (restriction on opening of the jaw), osteoradionecrosis, or breakdown of the mandible, loss of sensation, loss of taste, increased risk of dental caries (cavities), and decreased salivary function. Thus, quality of life can be severely compromised following the treatment of head and neck cancers. More concerning is the increase in non-cancer-related deaths in patients treated with concurrent high dose cisplatin and radiation in RTOG 91-11 as a result of long-term complications. This damage can occur anytime during radiation therapy and has been reported years after treatment. The long-term toxicities are a function of high dose radiation and volume of irradiated tissue, amplified by the addition of radio-sensitizing chemotherapy. Once the damage of normal tissue begins, it is usually progressive and irreversible. Because there is a 50-85% five year survival rate for patients treated for head and neck cancers, due in part to a rapidly increasing segment of younger patients experiencing HNSCC related to human papillomavirus infection, there are many people who are living with these long-term side effects (American Cancer Society, 2013 Statistics). Thus, the development of an effective radio-protector would improve the quality of life of many head and neck cancer patients.

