We will do a safety lead-in trial for head and neck cancer patients involving 6 subjects at the 28 mg/subject loading dose given by subcutaneous injection followed by one-half the loading dose (14mg/subject) administered by subcutaneous injection biweekly during the remainder of the trial. We will assess safety in a lead-in cohort of 6 head and neck cancer patients being treated with cisplatin and radiation therapy. Once those 6 subjects are enrolled, we will then move to full Phase 2 open enrollment. Based on the preclinical safety toxicology studies in mice and monkey and the results of the Phase 1 BMX-001 high-grade glioma trial in humans, we anticipate that a dose of 28 mg/subject load followed by one-half the loading dose (14 mgs) twice weekly will not have dose-limiting toxicities in patients enrolled in this study. If this expectation is confirmed (meaning there are no definite BMX-001-related dose-limiting toxicities, defined as grade 3 study-drug-related adverse events), this dose will be utilized in the full Phase 2 trial enrolling an additional 42 subjects. If one or more definite BMX-001 related grade 4 or 5 DLTs occur in the 6 patient safety lead-in cohort, accrual will pause pending review by the sponsor and DSMB. Non

BMX-001 related DLTs are anticipated in this patient population due to the primary disease and treatment regimen.

This is not a randomized trial. All eligible patients enrolled will receive BMX-001.

A maximum of 48 patients will be enrolled in this Phase 2 clinical trial.

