13.3 Follow-up Period

The follow-up period will consist of an approximately 24-month period following the end of RT treatment.

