13.4.2 Follow-up Requirements for Early Withdrawal

Subjects who prematurely withdraw due to toxicity or progressive disease will be followed for six months after a subject is removed from the study. End of study requirements outlined above will be conducted. Subjects withdrawn for pregnancy will be followed until the pregnancy is ended.

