13.5 End of Treatment

The end of treatment will occur when the patient comes off of study for the following reasons: completion of all study tests/procedures (approximately 24 months following completion of RT), progressive disease, unacceptable toxicity, allergic reaction to chemotherapy, allergic reactions to BMX-001, non-compliance with study follow-up, or withdrawal of consent. Patients will be followed for a minimum of 30 days after End of Treatment, and also followed for any unresolved adverse events considered related to study therapy. Patient death due to progressive disease will not be reported as a SAE.

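### Median overall survival will very probably not be reached in about 26 months of observation, and no 24-month survival rate or confidence interval is planned

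*Combined protocol and SAP*

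**What the plan says.** Overall survival (OS) is part of the first Phase 2 secondary objective (sections 5.3.1 and 16.2.2.2). The analysis is a Kaplan-Meier curve, "with overall survival censored at last follow-up if the patient remained alive", and the summaries are fixed as follows: "Median OS and PFS, as well as 6- and 12-month estimates of OS and PFS will be estimated from the Kaplan-Meier curve". No confidence interval is given for any survival estimate, although the radiographic response rate in the same section has one. Nothing is said about a median that is not reached.

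On expected survival, the introduction (section 4.1.2) has only a general figure: "Because there is a 50-85% five year survival rate for patients treated for head and neck cancers". Section 16.2.4 makes no survival assumption.

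On follow-up, section 13.3 says: "The follow-up period will consist of an approximately 24-month period following the end of RT treatment". Section 13.5 puts completion of study procedures at about the same time. Other sections allow less:

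- Section 13.4.2: "Subjects who prematurely withdraw due to toxicity or progressive disease will be followed for six months after a subject is removed from the study".
- Section 13.5 counts progression and unacceptable toxicity among the reasons for coming off study, with at least 30 days of follow-up afterwards.
- Footnote b to the schedule in section 13 lists minimum post-therapy visits within 1 month and at 6 and 12 months only.

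**The concern.** If about half or more of the patients live five years, half of them will not have died in a little over two years. The planned median would then be reported as not reached. What remains in the list is the 6- and 12-month rates, early points at which nearly everyone is expected to be alive and at which good and poor prognosis look much alike.

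Improved survival through tumor control is part of the rationale (section 4.4.1), and possible tumor protection by the drug is a stated concern of the data and safety monitoring board (section 14.3). A survival summary that says little about either is a missed opportunity. A 24-month figure chosen after the data are seen would be weaker than one fixed in advance.

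**Working it through.** **The plan's own figure.** No event count, power or survival assumption is stated for OS. The only design figure is the width of the two-sided 95% Clopper-Pearson interval for n = 40 at 0.50. For 20/40 the limits are 0.338 and 0.662, width 0.324, which agrees with section 16.2.4.

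**Inputs.**
- Five-year survival S5 = 0.50 to 0.85 (section 4.1.2).
- Observation: about 24 months after RT (section 13.3) plus the treatment period (section 13.1.1: "The treatment period consists of 6-7 weeks of concurrent RT and chemotherapy with BMX-001"), so about 25.5-26 months from treatment start.
- Sample size 48 (section 4.3.2: "A maximum of 48 patients will be enrolled in this Phase 2 clinical trial").

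**Expected survival.** Under constant hazard, an assumption, S(t) = S5^(t/60) with t in months:

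| S5 | 6 mo | 12 mo | 24 mo | 26 mo | Deaths by 26 mo, of 48 | Median |
|---|---|---|---|---|---|---|
| 0.50 | 0.933 | 0.871 | 0.758 | 0.741 | about 12 | 60 mo |
| 0.85 | 0.984 | 0.968 | 0.937 | 0.932 | about 3 | 256 mo |

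The median is 60 × ln(0.5)/ln(S5). With complete follow-up the curve reaches 0.50 only after 24 of 48 deaths.

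**Chance of reaching the median.** P(deaths ≥ 24) with deaths ~ Bin(48, 1 − S(26)):

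- S5 = 0.50: 0.0003 (0.001 with n = 40).
- S5 = 0.85: essentially 0.

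**Sensitivity to the shape of the curve.** Keep S5 = 0.50 and let a share f of the five-year deaths fall before month 26, so S(26) = 1 − 0.5f. Constant hazard corresponds to f = 0.259/0.5 = 0.52.

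| f | S(26) | Chance |
|---|---|---|
| 0.60 | 0.70 | 0.003 |
| 0.80 | 0.60 | 0.10 |
| 0.90 | 0.55 | 0.29 |
| 1.00 | 0.50 | 0.56 |

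**Sensitivity to a worse prognosis than quoted** (assumption, constant hazard): S5 = 0.40 gives S(26) = 0.672 and a chance of 0.01; S5 = 0.30 gives 0.593 and 0.12.

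**What a 24-month rate adds.** The two ends of the quoted range differ by 0.968 − 0.871 = 0.097 at 12 months and by 0.937 − 0.758 = 0.179 at 24 months. Exact 95% intervals at 24 months with complete follow-up are 0.604-0.864 for 36/48 alive and 0.828-0.987 for 45/48 alive.

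**What early end of follow-up does to it.** Simulation with 2,000 runs of 48 patients and S5 = 0.50. Assumptions: constant progression hazard, no death without progression, mean survival after progression of 12 months. True 24-month OS in this model is 0.824; it exceeds 0.758 because deaths come only after progression.

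| Follow-up after progression | Mean 24-month Kaplan-Meier estimate |
|---|---|
| To month 26 | 0.823 |
| 6 months | 0.885 |
| 1 month | 0.973 |

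The shorter rules censor patients just when their risk of death is highest, so the censoring is informative and the estimate is too high.

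**The case against.** **The survival figure is background.** It covers head and neck cancer in general and is linked partly to younger patients with HPV-related disease. The trial requires high-risk features and stage III-IVB and excludes the more favorable stages (sections 6.1 and 6.2). This stands. A reader might infer that median OS cannot be estimated at all, since a survival curve never rises and five-year survival of 50% puts the median at 60 months or later. That is true of a population median if the quoted figure applies. The documents do not say it applies to this trial, and an estimate from 48 patients can still cross 0.50, as the sensitivity results show.

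**The second year is not discarded.** The Kaplan-Meier curve includes every later death and censoring time, and a 24-month value can be read from it. This also stands; the gap is in the pre-specified summaries and intervals.

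**The 6- and 12-month landmarks match the minimum visit schedule.** Correct, and for that reason a change to the analysis text alone would not be enough.

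**Progression-free survival (PFS).** A reader might extend the point to median PFS. The documents give no PFS rate, so nothing shows that it is out of reach. In section 5.3.1 the word median is attached to PFS, not OS.

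**Limited weight.** OS is descriptive, comes from a single-arm trial, and is not among the secondary endpoints listed in section 5.2. It is not the only check on tumor protection: PFS, response and board review also bear on it. A 24-month rate near 0.75 would have an interval about 0.26 wide, more than the 0.18 gap between the best and worst quoted prognosis. It informs, but does not settle benefit or harm.

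**Conclusion.** The point holds as a matter of probability. On the protocol's quoted survival and constant hazard, about 3 to 12 deaths are expected against about 24 needed, and the chance of reaching median OS is about 0.0003 at the lower end of the range. Only strongly front-loaded deaths (0.10-0.29 for 80-90% before month 26) or clearly worse survival than quoted (0.12 at 30%) make it appreciable. The listed 6- and 12-month OS rates sit where about 87-98% are expected alive, and no 24-month rate or interval is planned although follow-up is stated to last about 24 months after RT.

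The follow-up rules must be reconciled before a 24-month rate can be trusted. The size of the bias shown depends on the assumed 12-month survival after progression; its upward direction follows from censoring patients soon after progression, when their risk of death is raised. The change is worth making, but the primary endpoint and the stated interval width are unaffected.

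**What to change.** 1. In section 16.2.2.2, report Kaplan-Meier OS at 12 and 24 months with 95% confidence intervals (for example on the log-log scale). Give median OS only if the curve reaches 0.50, and otherwise state that it was not reached.
2. Reconcile sections 13.4.2, 13.5 and the schedule in section 13 with the 24-month follow-up in section 13.3. Collect vital status to month 24 for every treated patient, regardless of progression or withdrawal from treatment, unless consent is withdrawn.
3. In the same edit, state one starting point for OS. Section 13.7.1 counts from enrollment and section 16.2.2.2 from the start of treatment; this does not alter the result above.
4. Leave median PFS in section 5.3.1 as it is.

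The cost is a short protocol change and one vital-status contact or record check for patients no longer attending. No extra imaging or disease assessment is needed.
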